4.10.7 Suspected Unexpected Serious Adverse Reactions

A Suspected, Unexpected Serious Adverse Reaction (SUSAR) is a subset of SAEs that, although foreseeable, are potentially related to the IMP and not identified in the reference safety information and will be reported to the appropriate regulatory authorities and investigators following local and global guidelines and requirements. The identification and reporting of SUSARs is the responsibility of Zambon’s Pharmacovigilance department. Following database lock, a listing of SUSARs will be requested from Zambon. If any occurred during the study, they will be incorporated in the TLFs.

The following summaries will be provided:

- A summary of number and proportion of subjects reporting at least one SUSAR. The corresponding two-sided 95% CI of the proportion for each treatment group using the Clopper-Pearson method
- A summary of number and percentage of subjects reporting at least one SUSAR, and the number of SUSARs presented by System Organ Class, and Preferred Term.

A by-subject listing of SUSARs will be provided.

4.11 Determination of Sample Size

This study has been powered to reach statistical significance for the superiority comparisons of N-acetyl cysteine (NAC) vs. placebo (primary study objective), and for the non-inferiority comparisons of NAC vs. ambroxol hydrochloride (key secondary study objective) in at least one of the two co-primary endpoints at the end of the 1-week treatment. This implies that sample size computation must account for the type I error inflation caused by the multiplicity over the two co-primary endpoints and by the multiplicity over the study targets (superiority and non-inferiority assessments) as well as the logical relationships among the two family of hypotheses with the non-inferiority testable only provided that the superiority contrast, assessed on the same endpoint, is statistically significant. To accomplish this, a multiple-sequence gatekeeping procedure [21] was implemented in a Monte Carlo (MC) study with 1000 runs and with the Bonferroni correction applied to the set of superiority comparisons (first gatekeeper) and

the Hochberg correction applied to the set of non-inferiority comparisons (second gatekeeper) in order to control the overall type I family-wise error rate at the one-tailed 0.025 significance level. Details on the adopted gatekeeping strategy are reported further on.

For the superiority tests, and with group sample sizes of 100 patients in placebo group and 100 patients in NAC group, the Monte Carlo study estimated an overall power (“disjunctive” power) close to 93% to reach statistical significance in at least one co-primary end-point. These calculations are based on a one-sided Mann-Whitney test and assuming a minimal clinically relevant difference of 0.35 points between placebo and NAC on a 0-3-point scale, standard deviation equal to 0.79 and 0.77 for sputum viscosity and expectoration difficulty scores (change from baseline to the 1-week treatment) respectively and a correlation between the two end-points equal to 0.31.

For the non-inferiority tests, a sample of 100 patients per each active treatment group ensures sufficient disjunctive power (Monte Carlo disjunctive power = 82%) to detect non-inferiority between NAC and ambroxol in at least one co-primary end-point. These calculations are based on a one-sided non-inferiority t-test assuming a margin of non-inferiority equal to 0.30, standard deviation equal to 0.79 and 0.77 for sputum viscosity and expectoration difficulty scores (change from baseline to the 1-week treatment) respectively and a correlation between the two endpoints equal to 0.31.

Assuming a drop-out rate of about 10% over one week of entry, a total of 333 patients will be randomized (i.e. 111 patients in the placebo group, 111 patients in the NAC group and 111 patients in the ambroxol group).

4.12 Changes to protocol-defined analyses

The following changes from protocol defined analyses were made:

- In protocol, a test of site-by-treatment interaction was planned to be carried-out using a two-way nonparametric ANOVA performed by resorting to the “Aligned Rank Transform” (ART) procedure. However, this ART procedure will not be performed in final analysis. The main reason is due to the program limitation for implementing in the SAS 9.4 and no existing and validated procedure to perform this ART analysis. From the program maintenance and quality control perspective, the study team decides to use canonical two-way nonparametric ANOVA procedure instead.

4.14 Appendix

4.14.1 Hochberg procedure

In the case the co-primary endpoints for the superiority of NAC versus placebo are statistically significant (first gatekeeper), in the second gatekeeper for the family of non-inferiority tests the Hochberg procedure for adjustment of multiple comparisons across the two co-primary endpoints will be performed. The Hochberg procedure assumes p-values are independent and uniformly distributed under respective null hypotheses and control the familywise error rate calculated in step-up fashion.

Suppose test m null hypotheses and denote the ordered p-values as $p_{(1)} \leq \dots \leq p_{(m)}$, the Hochberg-adjusted p-values $\tilde{p}_{(1)} \leq \dots \leq \tilde{p}_{(m)}$ are obtained from:

$$\tilde{p}_{(i)} = \begin{cases} p_{(m)} & \text{for } i = m \\ \min(\tilde{p}_{(i+1)}, (m - i + 1)p_{(i)}) & \text{for } i = m - 1, \dots, 1 \end{cases}$$

The SAS syntax of Hochberg procedure is specified as follows:

```
PROC MULTTEST INPVVALUES=<input_raw_pvalue> OUT=<output_adjust_pvalue>
HOCHBERG;
RUN;
```

Where `input_raw_pvalue`= “the raw p-value calculated”.
`output_adjust_pvalue`= “the adjusted p-value output”.

The procedure of MULTTEST will compute the adjusted p-value and can be tested on both co-primary endpoints with an overall probability α set to 0.025 (one-tailed).

4.14.3 Two-way nonparametric ANOVA procedure

A test of site-by-treatment interaction will be carried-out using a two-way nonparametric ANOVA and modelling adjustment for covariates will be performed and tested at two-tailed $\alpha=0.1$ by including treatment, site, and site-by-treatment interaction terms in the model. SAS syntax can be referred as follow:

```
PROC RANK DATA=<input_dataset> OUT=<ranked_dataset>;  
  BY SITE;  
  VAR response;  
  RANKS ranked_response;  
RUN;  
  
PROC ANOVA DATA=<ranked_dataset>;  
  CLASS site trt01pn;  
  MODEL ranked_response = site trt01pn site* trt01pn;
```

RUN;

To obtain the treatment difference by site for the forest plot, SAS syntax can be referred as below:

```
PROC GLM DATA=<ranked_dataset>;
  CLASS site trt01pn ;
  MODEL ranked_response = site trt01pn site* trt01pn;
  LSMEANS site*trt01pn /cl PDIFF STDERR;
RUN;
```

Where trt01pn = “treatment group, 1 stands for test group; 2 stands for control group”.

response = “change from baseline to day 7 in Sputum viscosity” or “change from baseline to day 7 in Expectoration difficulty”

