9. CLINICAL TRIAL POPULATION

9.1. NUMBER OF SUBJECTS

A total of 333 subjects (111 in each treatment group) is planned to be enrolled into the trial. The enrolment is competitive among sites.

For a description of sample size calculation, please refer to [Section 20.3](#).

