4.9.4 Multi-center Analysis

CCI In the first instance, since the aim of the analysis is to examine sites, the analysis will be performed using individual

sites (i.e. no pooling of sites). If the situation occurs where there are convergence issues or SAS errors/warnings due to some sites with small numbers of subjects, sites with 8 or fewer randomized subjects will be grouped for the multi-center analysis.

The following summaries will be provided for each co-primary efficacy endpoint:

- A summary of the change from baseline to day 7 in sputum viscosity score using the mITT population, in which the missing data will be handled using the MVTF. Two-way non-parametric ANOVA will be performed by including treatment, site, and site-by-treatment interaction terms in the model.
- A summary of the change from baseline to day 7 in expectoration difficulty score using the mITT population, in which the missing data will be handled using the MVTF. Two-way non-parametric ANOVA will be performed by including treatment, site, and site-by-treatment interaction terms in the model.

Forest plots will be generated to display the results at each center. Note that the Forest plots utilize a GLM fit to the ranked datasets used by the two-way non-parametric ANOVA. This is because it is not possible to include an interaction term (site-by-treatment) into the stratified Mann-Whitney U Statistic test utilized for analysis of the co-primary endpoints. Caution must be taken in interpreting the results of the multi-center analysis owing to difference in statistical methodology compared to the primary and secondary endpoints analysis as well as a lack of appropriate stratification for the randomization.

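### The site-by-treatment check ranks scores within each site, so the interaction test is miscalibrated and the forest plot is not comparable across sites when site sizes differ

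*SAP*

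**What the plan says.** SAP 4.14.3 gives the code. The ranking step "PROC RANK DATA=<input_dataset> OUT=<ranked_dataset>" carries a `BY SITE` statement, so the change scores are ranked separately in each site. The ranks go into "PROC ANOVA DATA=<ranked_dataset>" with the model "MODEL ranked_response = site trt01pn site* trt01pn", and the interaction is tested at a two-tailed 0.10 level (SAP 4.9.1.1). Treatment has two levels: "treatment group, 1 stands for test group; 2 stands for control group".

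The forest plot takes "LSMEANS site*trt01pn /cl PDIFF STDERR" from a PROC GLM fit to the same ranks. SAP 4.9.4 confirms this: "the Forest plots utilize a GLM fit to the ranked datasets used by the two-way non-parametric ANOVA".

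Sites are analysed individually at first. Those with 8 or fewer randomised subjects are grouped only if there are convergence problems or SAS errors or warnings (SAP 4.9.1.1, 4.9.4). About 25 sites and 333 patients are planned (SAP 3.1), and Protocol 9.1 states: "The enrolment is competitive among sites".

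SAP 4.12 explains that a standard two-way nonparametric ANOVA replaces the aligned rank transform of Protocol 20.4.6. Neither it nor SAP 4.9.1.1 or 4.9.1.2 mentions ranking within site. The caution in SAP 4.9.4 concerns the difference in methodology and the stratification of the randomisation, not site size.

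**The concern.** Within-site ranks run from 1 to N, so a site of 40 and a site of 6 are on different scales when they enter one model with one residual variance. This has two consequences.

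- **Test.** The pooled residual is dominated by the large sites, which hides differences among small ones. A common effect also becomes a different rank difference at each site size, which the model reads as interaction if the effect is large.
- **Plot.** Larger sites show larger differences even when the effect is the same everywhere, so a reader could conclude that large centres drive the result.

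The trial is meant as pivotal evidence for registration, and these are the between-centre checks visible in the plan. The stratified test in SAP 4.14.5 avoids the problem: it divides each stratum's comparison by the product of the two arm sizes, which puts it on a probability scale before the strata are combined. SAP 4.14.3 has no such step.

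**Working it through.** **Inputs.** Ranking step, model, LS-mean differences and two groups: SAP 4.14.3. Level 0.10: SAP 4.9.1.1. About 25 sites: SAP 3.1. 111 per arm, effect 0.35, SDs 0.79 and 0.77, correlation 0.31: SAP 4.11. Site sizes are not in the documents and are assumed below. Two arms give 222 patients, or 222/25 = 8.9 per site on average.

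**1. The plan's own figures.** The plan gives no result for the interaction test beyond its level. Its power inputs do reproduce. With 100 per group, 0.35/0.79 × √50 = 3.13 and 0.35/0.77 × √50 = 3.21, against a critical value of 2.24 (one-sided 0.0125). Single-endpoint power is 81% and 83%. With correlation 0.31 the chance of at least one success is 94.6%, or 93.6% with a Mann-Whitney efficiency of 0.955. The stated figure is close to 93%. The non-inferiority power comes out at 81.9% against the stated 82%.

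**2. Scale of within-site ranks.** Take a site with m and n patients in the two arms, N = m + n. Let p be the probability index, with ties counted half. The mean ranks are (m+1)/2 + n·p and (n+1)/2 + m·(1−p), so

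difference = N × (p − 0.5).

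At p = 0.60 this is 0.4 at N=4, 1.2 at N=12, 3.0 at N=30 and 4.2 at N=42. The site's mean rank is always (N+1)/2, so the site term carries only site size. Without ties the rank variance is (N²−1)/12: 1.25 at N=4 and about 147 at N=42. That is why large sites dominate the residual.

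**3. Forest plot.** Simulation with 25 sites, 0–3 scores, baseline 2 or 3, and the same raw effect of about 0.37 everywhere. Mean within-site rank difference:

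| N | 4 | 6 | 8 | 12 | 18 | 30 | 42 (skewed layout) |
|---|---|---|---|---|---|---|---|
| Difference | 0.51 | 0.76 | 1.02 | 1.54 | 2.28 | 3.79 | 5.36 |

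The ratio to N=4 is 3.79/0.51 = 7.4 at N=30. At N=42 it is 5.36/0.52 = 10.3, where 0.52 is the N=4 value in that layout. Ranked over all patients, the difference stays between about 27 and 31 at every size.

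**4. Interaction test.** Same simulation, 2,000 runs, percentage rejecting at 0.10, given as coded ranks / overall ranks. Heterogeneity SDs and the effect of 1.0 are on the latent scale.

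| Scenario | Sizes 8–9 | Sizes 4–30 | Sizes 4–42 |
|---|---|---|---|
| No effect | 9.4 / 11.2 | 0.2 / 9.0 | 0.0 / 10.2 |
| Common effect, about 0.37 | 6.4 / 9.4 | 1.4 / 9.6 | 0.4 / 8.8 |
| Common effect, 1.0 | 2.9 / 10.1 | 37.8 / 10.4 | 41.2 / 11.3 |
| Effect SD 0.4 | 42.6 / 52.0 | 17.3 / 54.3 | 12.0 / 49.8 |
| Effect SD 0.8 | 95.2 / 96.7 | 58.4 / 96.2 | 43.5 / 93.1 |
| Effect only at sites under 18 | n/a | 1.3 / 79.3 | 0.2 / 73.8 |
| Effect only at sites of 18 or more | n/a | 80.9 / 82.0 | 67.6 / 81.6 |

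Further runs at an effect SD of 0.6 gave about 29% to 42% against 76% to 78% for sizes 4–40 or 4–16, and 73% against 80% for sizes 8–10. Across runs with very unequal sites, a large common effect gave a false interaction about 34% to 45% of the time.

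**5. PROC ANOVA against PROC GLM.** Marginal and partial sums of squares gave near-identical rejection rates: at most about 1 percentage point apart in the near-equal layout, and equal to the printed precision in the other two.

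**6. The remedy when site levels differ.** With site-level shifts of SD 0.4 (sizes 4–30, common effect about 0.37), overall ranks reject 10.6% and the coded ranks 1.8%. With shifts of SD 1.0, overall ranks reject 12% to 14% at an effect of 0.35 and about 28% to 33% at an effect of 1.0. Part of this comes from the floor and ceiling of the scale.

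**The case against.** The strongest reply is that the size of the problem depends on site sizes the documents do not give. Competitive enrolment supports unequal sizes but no particular range, and with near-equal sites the loss is modest. That stands, and every figure for unequal sites is conditional on the assumed layout. The scaling with N is not conditional: it follows from the code.

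A reader might infer that the check would almost always report no interaction. The results do not support that. At an effect SD of 0.8 the coded test still finds heterogeneity 44% to 58% of the time in the unequal layouts. Heterogeneity confined to large sites is mostly found, and with a large common effect the error runs the other way.

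A reader might also treat PROC ANOVA with unbalanced cells as a serious error. Randomisation is blocked within site (Protocol 13.3), which favours similar arm sizes, and the comparison in step 5 shows no material difference. PROC GLM is good practice here, not a correction that changes the result.

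Within-site ranking does remove site main effects, which overall ranking does not. This too stands, and it is a real cost of the remedy (step 6).

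Grouping sites of 8 or fewer is no safeguard. It applies only after SAS or convergence problems, and it would create one larger pseudo-site with a longer rank range. Some text in SAP 4.9.1.1 and 4.9.4 is blacked out, so further explanation there cannot be excluded, but the code is fully visible.

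**Conclusion.** The point holds as a fault in a supporting analysis. Ranks taken within site and left unstandardised make each site's difference proportional to its size. If sizes are unequal, the test does not hold its 10% level: it is too conservative with small or moderate common effects and can signal a false interaction with a large one. It loses much power and misses heterogeneity confined to small sites. The forest plot enlarges an identical effect about 7- to 10-fold between N=4 and N=30 to 42. With near-equal sites the power loss is small.

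The sizes rest on assumed site layouts, on two-arm comparisons and on simulated 0–3 scores. It would be wrong to infer that the efficacy conclusion is at risk. Protocol 20.4.6 calls this an additional analysis, and neither the primary test nor the multiplicity procedure in SAP 4.9.1.4 uses it.

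**What to change.** - Delete the `BY SITE` statement in SAP 4.14.3 so that ranks are taken over all patients in the comparison.
- Test site*trt01pn in PROC GLM, which the next code block already uses.
- In the forest plot, show site-specific differences in mean change or in win probability, with confidence intervals, and align the text of SAP 4.9.4.

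The cost is a small change to code and plot scale, on the same data, recorded as a SAP amendment. The downside should be stated in the SAP: overall ranks no longer remove site main effects, so the test can over-reject if site levels differ widely and the effect is large. A significant interaction should therefore be read alongside the site-level plot on the new scale.

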4.14.4 EM Algorithm

The expectation-maximization (EM) algorithm is a technique for maximum likelihood estimation in parametric models for incomplete data. The EM algorithm computes the MLE for the means and covariance matrix, of a multivariate normal distribution from the input data set with missing values.

The SAS syntax of EM algorithm is specified as follows:

```
PROC MI DATA=<input_dataset> SEED= <Seed number> NIMPUTE=0;
  EM OUTEM=<out_data>;
  VAR spv epd spc cough sv;
RUN;
```

Please note that the imputed values will round to the nearest integer. For value range of sputum viscosity, expectoration difficulty, sputum color and cough severity score will be integer from 0 to 3. The range of Sputum volume imputed value can be non-negative number.

Where input_data= “Individual efficacy data”

Seed number= “Random Seed”
spv=“Sputum viscosity”
epd=“Expectoration difficulty”
spc=“Sputum Color”
cough = “Cough severity score”
sv=“sputum volume”

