20.4.4. HANDLING OF MISSING DATA

Missing data on the primary and secondary efficacy endpoints will be imputed as treatment failures (MVTF) by replacing missing values with the scores recorded at baseline or last measurement, whichever is worse as primary imputation method. Expectation-maximization (EM) algorithm and

last observation carried forward (LOCF) will also be used as sensitivity analyses. Details regarding the EM algorithm (i.e. the randomization seed and the SAS code that will be used) will be reported in the SAP.

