4.9.1.3 Handling of Dropouts or Missing Data

Missing data on the primary and secondary efficacy endpoints will be imputed as treatment failures (MVTF) by replacing missing values using worst observation carried forward

(WOCF) with the worst scores recorded at baseline or post baseline (follow up) (including measurements from the premature discontinuation visit) imputed to missing visits. MVTF is the primary imputation method. The Expectation-Maximization (EM) algorithm and last observation carried forward (LOCF) will be used as sensitivity analyses. Data missing at baseline will not be imputed.

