- A summary of the change from baseline to day 7 in sputum viscosity score using the PP population, in which the missing data will be handled using the MVTF
- A summary of the change from baseline to day 7 in expectoration difficulty score using the PP population, in which the missing data will be handled using the MVTF

The following sensitivity analyses will be provided:

- A summary of p-value of the superiority and non-inferiority tests for the change from baseline to day 7 in sputum viscosity score using the mITT population and PP population, in which the missing data will be handled using the EM algorithm
- A summary of p-value of the superiority and non-inferiority tests for the change from baseline to day 7 in expectoration difficulty score using the mITT population and PP population, in which the missing data will be handled using the EM algorithm
- A summary of p-value of the superiority and non-inferiority tests for the change from baseline to day 7 in sputum viscosity score using the mITT population and PP population, in which the missing data will be handled using the LOCF
- A summary of p-value of the superiority and non-inferiority tests for the change from baseline to day 7 in expectoration difficulty score using the mITT population and PP population, in which the missing data will be handled using the LOCF

The test statistics for the superiority and non-inferiority tests can be found in the Appendix (Section 4.14.5 and 4.14.6).

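### The printed EM sensitivity model leaves out treatment arm and earlier visits, so it is a poor check on the non-inferiority result

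*SAP*

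**What the plan says.** SAP 4.9.1.3 makes worst observation carried forward (WOCF, treating missing values as failures) the primary imputation and adds: "The Expectation-Maximization (EM) algorithm and last observation carried forward (LOCF) will be used as sensitivity analyses". SAP 4.9.2 lists the EM output for viscosity as "A summary of p-value of the superiority and non-inferiority tests for the change from baseline to day 7 in sputum viscosity score", in both the mITT and PP populations, with a matching entry for expectoration difficulty.

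The model itself is in SAP 4.14.4. The variable list is "VAR spv epd spc cough sv": sputum viscosity, expectoration difficulty, colour, cough and volume, each defined without a visit. There is no treatment variable, no BY statement and no separate baseline or Day 3 variable. The procedure options are "SEED= <Seed number> NIMPUTE=0", the requested output is "EM OUTEM=<out_data>", and the input file is described only as "Individual efficacy data". On rounding: "Please note that the imputed values will round to the nearest integer".

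Protocol 20.4.4 says the SAP will report "the randomization seed and the SAS code that will be used", so this listing is the specification and not an illustration.

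**The concern.** EM fills a missing value with its expectation given what was observed on the same record. Suppose a patient leaves before Day 7 with no usable discontinuation assessment. If the record holds one visit, all five listed variables are missing and nothing is left to condition on. The fill is then the overall mean, pooled over the three arms, and also over visits if the file is stacked by visit. After rounding it is one integer for every such patient, even where Day 3 scores exist.

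Giving NAC and ambroxol patients the same score pulls the two arms together when they lose similar numbers. In a superiority comparison that is conservative: 0.35 × 0.9 = 0.315 at 10% drop-out. In a non-inferiority comparison it helps the test drug. What is at stake is the value of the EM p-values as support for the key secondary claim.

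**Working it through.** **The plan's own figures first.** Inputs from SAP 4.11: SDs 0.79 and 0.77, endpoint correlation 0.31, difference from placebo 0.35, margin 0.30, 100 evaluable per arm, about 10% drop-out, 111 randomised per arm. With NAC equal to ambroxol and the sequential rules of SAP 4.9.1.4, simulation gives superiority power of 93.2% (stated: close to 93%). Non-inferiority power is 81.1% if superiority is tested by t-test and 79.5% if by Mann-Whitney (stated: 82%). 100/0.9 = 111.1, against 111. These figures reproduce adequately. The documents give no operating figure for the EM analysis.

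**What a fully missing record receives.** In a small EM run with five correlated variables, every record missing all five received one identical value, the pooled mean. Records missing only the first variable received values from 0.22 to 1.71.

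**Shrinkage.** Let d_N and d_A be the fully missing fractions, μ_N and μ_A the Day 7 means, and c the common fill, with drop-out unrelated to outcome. The analysed difference is

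(1−d_N)μ_N − (1−d_A)μ_A + (d_N−d_A)c.

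If d_N = d_A = d, it is (1−d)(μ_N−μ_A): 0.30 becomes 0.27 at 10% and 0.24 at 20%. Baselines cancel in expectation under randomisation.

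**False non-inferiority, closed form** (SD 0.79, 111 per arm, true deficit 0.30, one-sided 0.025).
- Pooled fill, 10%: SE = √(2 × 0.9 × 0.79²/111) = 0.1006; shift = 0.03/0.1006 = 0.298; P(Z > 1.96 − 0.298) = 4.8%.
- Pooled fill, 20%: SE = √(2 × 0.8 × 0.79²/111) = 0.0948; shift = 0.06/0.0948 = 0.633; P(Z > 1.327) = 9.2%.
- By-arm mean as a single unrounded value: no shrinkage, but the estimated SE is (1−d) times the true SE, so P(Z > 1.96 × 0.9) = 3.9% at 10% and P(Z > 1.96 × 0.8) = 5.8% at 20%.
- Pooled fill, 10%, at the per-endpoint 0.0125: 2.6%.

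**False non-inferiority, simulated** with the SAP 4.14.6 statistic and its margin conversion. There were 4,000 runs per scenario; the Monte Carlo SE is √(0.05 × 0.95/4000), about 0.3 points. Assumptions not in the documents: baseline 2 or 3 equally likely, latent Day 3-Day 7 correlation 0.6, mean ambroxol change −1.0 or −1.3, equal drop-out that is random or depends on Day 3.

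| Ambroxol change, drop-out | Complete | Pooled fill | By arm with baseline and Day 3, single rounded fill | WOCF |
|---|---|---|---|---|
| −1.0, 10% random | 2.7% | 5.6% | 4.4% | 5.7% |
| −1.0, 10% by Day 3 | 2.6% | 4.6% | 3.8% | 4.6% |
| −1.0, 20% random | 2.7% | 10.2% | 5.6% | 9.4% |
| −1.3, 10% random | 2.9% | 5.3% | 4.5% | 5.0% |
| −1.3, 10% by Day 3 | 2.6% | 5.6% | 4.5% | 3.9% |
| −1.3, 20% random | 2.8% | 9.4% | 6.7% | 8.5% |

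Further runs put the pooled fill at 5.1-5.7% and a by-arm single rounded fill at 4.5-5.2% at 10%. Multiple imputation by arm from baseline and Day 3 gave 2.8% at 10% and 2.5% at 20%.

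**Unequal drop-out.** Take μ_N = 1.8, μ_A = 1.5, d_N = 20%, d_A = 5%.
- Fill 2: (0.8 × 1.8 + 0.2 × 2) − (0.95 × 1.5 + 0.05 × 2) = 1.840 − 1.525 = 0.315, against NAC.
- Fill 1: 1.640 − 1.475 = 0.165, strongly for NAC.

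The sign turns on one rounding step.

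**The case against.** Five points have force.

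1. Not every drop-out is missing everything. Protocol 10.10 and 10.11 ask for the Visit 4 evaluations at discontinuation, and 11.1.5 asks for a rating that day where possible. SAP 4.9.1.3 mentions these data for WOCF but not for EM. If half of drop-outs had usable ratings, the pooled fill would give 3.7-4.5% at 10%. The file layout is also unstated. So the common score applies to fully missing records, not to all drop-outs.

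2. A reader might infer that the analysis always leans towards non-inferiority. It does not. With 20% NAC and 5% ambroxol drop-out, rejection was 1.9% or 6.9%, depending on the assumed response level. With 20% and 10%, it was 3.5-4.5% when the fill was 2 and 13-18% when it was almost always 1. A figure such as 13% is therefore one scenario.

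3. Much of the inflation is due to single rounded filling. In one set of runs at 10%, a simple by-arm mean, rounded, gave 4.4-5.9% against 4.5-5.9% for the pooled fill. This stands, and it means that adding a BY statement alone is not a cure.

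4. A reader might take these rates as the trial's type I error. They are single-endpoint rates of a supporting table. Non-inferiority is decided on WOCF data in both mITT and PP, after superiority and with multiplicity control. Day 3 scores are also used by WOCF and LOCF.

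5. The code needs rewriting anyway: with zero imputations and only the parameter data set saved, it does not show how filled values are produced. True, but repairing the output would leave the model fault in place.

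**Conclusion.** The specification fault is established from the text: no arm, no baseline and no Day 3 score in the EM model. At the planned 10% equal drop-out, the false non-inferiority rate of this sensitivity test roughly doubles, from about 2.5-3% to about 4.6-5.7%; at an assumed 20% it is about 9-10%. A by-arm single fill still gives about 3.8-5.2% at 10%, so the missing arm and visit terms account for only part of the excess.

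The main consequence is weak corroboration. WOCF, the method being checked, takes 0.30 to about 0.27 in the same 10% setting (3.9-5.7%). A second method with similar shrinkage cannot expose the first. The sizes rest on records missing all five values, a file of one visit per record not run by arm, and the assumed score distributions and drop-out mechanisms. The direction holds for equal drop-out only. This should be corrected, but it does not undermine the primary analysis.

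**What to change.** Rewrite SAP 4.14.4 as follows:
- Use one record per patient, with baseline, Day 3 and Day 7 values of each measure as separate variables.
- State how assessments from the premature discontinuation and deterioration visits enter: as Day 7 values, as auxiliary variables, or not at all.
- Fit the model BY trt01pn.
- Replace the single rounded EM value with multiple imputation, for example 50 data sets. Analyse each with the 4.14.5 and 4.14.6 statistics and combine the results across imputations. State how draws are kept on the 0-3 scale.
- Amend SAP 4.9.1.3 and 4.9.2 to name this method, and record the departure from Protocol 20.4.4 in SAP 4.12.

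The cost is SAP wording and a few more lines of SAS; no new data are needed. The method still assumes that, within arm, missingness depends only on observed scores, and the SAP should say so.
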